### 3.3 STUDY DRUG EXPOSURE AND TREATMENT COMPLIANCE

Exposure will be analyzed by calculating the number of days with exposure to study drug. Descriptive summary statistics will be provided using the safety population.

The treatment compliance will be calculated as (the actual total dose / the expected total dose)  $\times 100$ , where:

- The actual total dose = (total number tablets of dispensed – total number of tablets returned)  $\times 5$  (Note: If tablets were not returned, the data will be considered missing.)
- The expected total dose = (last dose date – first dose date +1)  $\times 5$

The number of patients with an overall study treatment compliance <80%, between 80% and 120%, and >120% will be presented based on the safety population.

Treatment compliance for below time periods will be calculated and presented as the same categories as overall compliance:

- Day 1 to Week 4 [study day 1 to study day 28]
- Week 4 to Week 8 [study day 29 to study day 56]
- Week 8 to Week 12 [study day 57 to study day 84]
- Week 12 to Week16 [study day 85 to study day 112]

A subject level listing for study drug exposure (the first dose date, last dose date, duration of treatment) and compliance (including overall compliance and compliance by each time period defined above) will be presented.

Study drug dispensing and accountability will be listed as well.

### 3.4 SAFETY ANALYSIS

All safety analyses will be performed on the safety population. No inferential statistics will be performed; only summary statistics will be provided unless otherwise noted. Safety data will be presented by actual treatment group.

Safety variables include AEs, vital signs, 12-lead ECG, and clinical laboratory results.

#### Adverse Events

Adverse events will be coded to primary System Organ Class (SOC) and preferred term (PT) using MedDRA Version (Version 22.0).

TEAEs will be defined as AEs that are new or worsening after the first dose of study drug AEs with missing onset and end date will be considered as a TEAE. Serious adverse events (SAEs) are captured in the CRF and are determined by the investigator based on protocol section 10.1.1.2. Adverse events of special interest (AESIs) are recorded in the CRF and are defined in protocol section 10.1.1.3.

A general summary of patients with TEAEs, SAEs and AESIs will be tabulated with numbers and percentages of patients per treatment group. The number of AEs leading to withdrawal and SAEs leading to death will also be summarized.

The incidence of TEAEs will be reported as the number (percent) of subjects with TEAEs within SOC and PT. Subjects will be counted only once within a SOC and PT, even if the subject

experienced more than one TEAE within a specific SOC and PT. The number (percent) of subjects with TEAEs will also be summarized by severity (mild, moderate, or severe) and relationship (unrelated, unlikely related, possibly related, probably related, or definitely related) as captured in the CRF. The relationship of each AE to the study drug will be grouped as related (unlikely related, possibly related, probably related, or definitely related, missing) or unrelated.

The following incidence summary tables will be provided:

- All TEAEs
- All TEAEs by severity
- All TEAEs by relationship
- AEs with outcome of death
- Serious TEAEs
- Serious TEAEs related to study drug
- AEs leading to discontinuation of treatment
- All treatment emergent AESI

By subject listings for all AEs (including TEAE and non-TEAE), serious TEAE, treatment emergent AESI, related TEAE, AEs leading to study drug discontinuation, and AEs with an outcome of death will be provided.

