**Related to Study Drug (Possibly, Probably, or Definitely Related)**

Based on medical judgment, there is at least a reasonable possibility that the study drug caused the event; one or more of the following criteria apply:

- The event follows a reasonable temporal sequence from administration of study drug

- The event could not be reasonably attributed to the known characteristics of the patient's clinical state, environmental or toxic factors, or other modes of therapy administered to the patient
- The event follows a known pattern of response to study drug
- The event disappears or decreases on cessation or reduction in dose of the study drug. (It should be noted that in some situations an AE will not disappear or decrease in intensity upon discontinuation of study drug despite other clear indications of relatedness)
- The event reappears or worsens when the study drug is re-administered

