### **Unrelated to Study Drug (Unlikely or Unrelated)**

Based on medical judgment there is no reasonable possibility that the study drug caused the event; one or more of the following criteria apply:

- The event does not follow a reasonable temporal sequence from administration of study drug
- The event could be reasonably attributed to the known characteristics of the patient's clinical state, concurrent illness, environment or toxic factors, or other modes of therapy administered to the patient
- The event does not follow a known pattern of response to study drug
- The event does not disappear or decrease on cessation or reduction in dose of the study drug, and it does not reappear or worsen when the study drug is re-administered

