#### **11.2.2.7 Evaluation of Safety Endpoints**

Safety data will be analyzed using descriptive statistics and summaries by treatment group of SAEs, AEs, vital signs, clinical safety laboratory tests (hematology, coagulation, clinical chemistry, and urinalysis), and concomitant medication. Analyses will be performed using the safety analysis set.

Summaries of AEs (coded according to the MedDRA system organ class [SOC] and MedDRA preferred term) will include the following:

- Overview of the incidence of TEAEs (TEAEs, drug-related TEAEs, TEAEs leading to study discontinuation, and treatment-emergent SAEs)
- TEAEs by SOC and preferred term
- Intensity of TEAEs by SOC and preferred term
- Drug-related TEAEs by SOC and preferred term
- TEAEs leading to study discontinuation by SOC and preferred term
- Treatment-emergent SAEs by SOC and preferred term

Concomitant medication use during the treatment period will be summarized by Anatomical Therapeutic Chemical (ATC) class and World Health Organization (WHO) preferred name.

Summaries of vital signs will be presented. For each visit, the actual results, the change from Baseline, and the observed post-baseline value will be presented.

Summaries of clinical safety laboratory data will be presented. For each visit, the actual result, the change from Baseline, and the observed post-baseline value will be presented.

---

Data listings will be provided for each patient for all safety parameters.

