## **Sample Size**

Due to the exploratory nature of this study, no formal power calculations were used to determine the sample size. The number of subjects (46 patients in total, 23 patients per treatment group) was chosen based on clinical experience with other similar proof-of-concept studies.

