## **2.4 CHANGES TO THE STATISTICAL ANALYSIS FROM THE PROTOCOL**

Fibrosis and inflammation markers (FIB-4, APRI, and NALFD fibrosis score (NFS)) have been added as exploratory endpoints. Additional analyses may include analyses of subjects stratifying by baseline Fib-4 at 1.3. Pro-C3 results, indicating fibrosis, may also be available for analysis.

Physical examination (including general appearance, eyes, nose, throat, head/neck/thyroid, lymph nodes, cardiovascular, lungs/chest, abdomen, genitourinary, extremities, skin, musculoskeletal, neurologic, and other) as listed in protocol section 10.2.4 are not collected.

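### SAP 3.4 counts adverse events rated unlikely related as drug-related, while the protocol classes them as unrelated, so related-event outputs can only equal or exceed the protocol-defined counts

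*SAP*

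**What the plan says.** Protocol v3.0 section 10.1.1.5 sets out two classes of causality. One is headed "Related to Study Drug (Possibly, Probably, or Definitely Related"). The other is headed "Unrelated to Study Drug (Unlikely or Unrelated"), and its defining criterion is: "Based on medical judgment there is no reasonable possibility that the study drug caused the event".

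SAP 3.4 lists five relationship levels as captured on the CRF, from unrelated to definitely related, and plans a summary of TEAEs by relationship. It then says that the relationship "will be grouped as related (unlikely related, possibly related, probably related, or definitely related, missing) or unrelated". Only the plain unrelated rating is left outside the related group.

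The SAP outputs that name the related class are the table "Serious TEAEs related to study drug" and a by-subject listing of related TEAEs. Protocol 11.2.2.7 also plans an overview that includes drug-related TEAEs, and a table of "Drug-related TEAEs by SOC and preferred term".

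SAP section 1 says that the plan is based on protocol version 3.0. SAP 2.4, headed "CHANGES TO THE STATISTICAL ANALYSIS FROM THE PROTOCOL", covers added fibrosis markers, possible extra analyses and physical examination findings that were not collected. It does not mention causality.

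**The concern.** The same CRF rating falls in opposite classes in two current documents. An investigator who follows the protocol and ticks unlikely is recording that there is no reasonable possibility of drug causation. The SAP then reports that event as drug-related, so the label contradicts the recorded judgment.

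Safety and tolerability is a secondary objective, and SAP 3.4 limits safety to summary statistics. In a descriptive analysis the category label is the result, so a reader who applies the protocol's definition to the related-event outputs would misread them. The effect on the comparison between arms cannot be foreseen: unlikely events can occur on elobixibat and on placebo, so the regrouping could widen or narrow the difference.

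**Working it through.** The plan states no figure on this point, so there is none to reproduce. The check compares the two definitions and then works out what the difference does to patient counts.

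**1. The two definitions side by side**

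| Rating | Protocol 10.1.1.5 | SAP 3.4 |
|---|---|---|
| Definitely | related | related |
| Probably | related | related |
| Possibly | related | related |
| Unlikely | unrelated | **related** |
| Unrelated | unrelated | unrelated |
| Missing | no rule | related |

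The SAP's related set contains all of the protocol's related set plus two more members, unlikely and missing. Protocol 10.1.2 requires causality to be assessed for every AE and gives no rule for a missing value. Only the unlikely row is a contradiction.

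**2. Direction**

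Because one set contains the other, no event or patient can be related under the protocol and unrelated under the SAP. As a check, all 462 combinations of 0 to 5 events over the six categories were enumerated. The SAP result was below the protocol result in 0 of them, whether counting events or flagging the patient. The SAP event count was strictly higher in 336.

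**3. Size, counting patients**

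The tables count patients, so a patient changes class only if nothing stronger has been recorded. For a given type of event in one arm, let:

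- P = patients with at least one event rated possibly, probably or definitely;
- m = patients with none of those ratings but at least one event with missing causality;
- k = patients with none of those ratings, no missing causality, and at least one event rated unlikely.

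Then:

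- related under the protocol's stated categories = P
- related under the SAP = P + m + k
- related with unlikely moved to unrelated and missing kept as related = P + m

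The part due to the contradiction is therefore k, with k ≥ 0. The planned size is "46 patients in total, 23 patients per treatment group" (SAP 1.3 and protocol 11.1), so the shift in one arm's related rate is k/23:

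| k | k/23 | Shift (percentage points) |
|---|---|---|
| 0 | 0/23 | 0 |
| 1 | 1/23 | 4.3 |
| 2 | 2/23 | 8.7 |
| 3 | 3/23 | 13.0 |

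For illustration, assume P = 2 and m = 0 in one arm. The protocol rate is 2/23 = 8.7%. The SAP rate is 8.7% with k = 0, 3/23 = 13.0% with k = 1, 5/23 = 21.7% with k = 3 and 7/23 = 30.4% with k = 5. These values of P, m and k are assumptions, because the documents contain no event counts.

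**The case against.** The strongest reply is that the reach is narrow and the choice conservative. The SAP names only one table and one listing that clearly use the two-way grouping, and a listing reports no rate. The SAP's own list of tables omits the drug-related TEAE table that protocol 11.2.2.7 plans. If the SAP's list governs, the only tabulated rate affected is that of related serious TEAEs, where k may well be zero. The five-level summary keeps the unlikely rating visible, the same rule applies to both arms, and no test, efficacy result or AESI count is touched. A sponsor may also prefer to over-count related events, and counting missing causality as related leans the same way.

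Most of this stands as a limit on size. The five-level summary, on its natural reading, is unaffected, although the grouping sentence follows it directly and does not say which outputs it governs. Part of any excess over the protocol's categories may come from missing causality and not from the unlikely rating, which is why m and k are separated above.

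The contradiction itself remains. The five-level summary does not correct the related serious TEAE table or the related listing. A broader definition could be a legitimate choice, but it would have to be declared with a reason, and nothing in the SAP shows that it was deliberate. In the same subsection the SAP defers to the protocol's definitions of SAE and AESI and departs from its causality classes without comment. Treating missing causality as related fills a gap in the protocol. Treating unlikely as related overrides a class the protocol defines.

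**Conclusion.** The concern holds. SAP 3.4 is wrong as written against protocol 10.1.1.5, and the departure is undeclared. The direction is certain: related counts under the SAP equal or exceed the protocol-defined counts. The size is 4.3 percentage points of an arm's related rate for each patient whose strongest rating is unlikely, assuming the planned 23 patients in the arm. How many such patients there are, and how they divide between arms, cannot be learned from the documents. The effect is confined to descriptive safety outputs: the related serious TEAE table, the related-TEAE listing and any drug-related summary made under protocol 11.2.2.7. It should be corrected, but it does not bear on the primary analysis.

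**What to change.** In SAP 3.4, define related as possibly, probably or definitely related, with missing causality counted as related by a stated conservative default. Define unrelated as unlikely or unrelated. This matches protocol 10.1.1.5 for every category the protocol covers. Apply the definition to the related serious TEAE table, the related-TEAE listing and any drug-related TEAE summary under protocol 11.2.2.7. Keep the five-level summary by relationship as planned, and say that the two-way grouping does not apply to it.

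If the sponsor does want the broader grouping, the minimum is to list it in SAP 2.4 with a reason and label the affected outputs so that readers know unlikely events are included. The cost of alignment is one sentence in the SAP and one format statement in the programs.

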## **Vital Signs**

Evaluation of vital signs (systolic and diastolic blood pressure, pulse, respiratory rate and body temperature) will be performed at all visits. Vital signs will be summarized as actual value and change from baseline for each treatment group at each scheduled assessment.

A listing of all vital sign assessments will be presented.

## **12-Lead ECG**

ECG assessments are performed at the Screening visit and the EOT visits. Descriptive statistics for ECG parameters (Heart rate, PR Interval, QRS Interval, QT Interval and QTC Interval) and changes from baseline at each scheduled timepoint will be presented by treatment group.

A subject data listing will present changes from baseline in ECG results captured in the CRF (categorized as normal; abnormal, not clinically significant; and abnormal, clinically significant) to end of treatment.

## **Laboratory Tests**

Descriptive summaries of laboratory data (for clinical chemistry, hematology/coagulation, urinalysis, lipid profile, endocrinology, bile acids, serology, and other tests as listed in the Appendix) will be presented for the safety analysis set along with listings of lab data collected. Laboratory results at each scheduled visit will be summarized by actual treatment group, along

with changes from baseline to each post-baseline visit. Values outside of the reference range will be flagged in the listings.

Shift tables for the shift from baseline with respect to the reference normal range will be provided.

Laboratory abnormalities of special interest will be summarized.

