## **10.2.2 Individual Patient Safety Monitoring**

### **10.2.2.1 Liver Monitoring**

Strategies to monitor markers of liver disease throughout the study are outlined below where the ULN will be based on central laboratory reference values for age and gender. Patients will be monitored as described below for drug-induced liver injury from randomization to 2 weeks following the last administration of study drug.

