#### **Elevated ALT**

- ALT  $>5 \times$  ULN or  $>3 \times$  Baseline (if ALT elevated at Baseline): repeat AST, ALT, total bilirubin, alkaline phosphatase (ALP), and INR within 72 hours of receipt of the result and closely monitor the patient. If liver enzyme elevation is confirmed, interrupt the study drug. The study drug can be restarted only if a competing etiology is identified or liver tests return to Baseline.

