#### **11.2.2.1.2 Safety**

The safety endpoints for this study include clinical laboratory assessments, vital signs, AEs, ECGs, physical examinations, and concomitant medications.

AEs will be coded using the latest version of the Medical Dictionary for Regulatory Activities (MedRA). TEAEs will be defined as AEs that are new or worsening after the first dose of study drug. A general summary of patients with TEAEs and serious adverse events (SAEs) will be tabulated with numbers and percentages of patients and repeated for severity and relationship to study drug per treatment group. The number of AEs leading to withdrawal and SAEs leading to death will also be summarized. The incidence of TEAEs will be summarized by body system and treatment group.

The safety laboratory data will be summarized by visit and by treatment group, along with changes from Baseline. Values outside of the reference range will be flagged and laboratory abnormalities of special interest will be summarized.

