## Analysis Visit

Visit-based data summaries will be presented by analysis visits. A window assessment will be performed according to the below table for any subject that missed a planned visit (on both efficacy and safety endpoints). The purpose of using this analysis window is to include potential unscheduled visits when a subject missed the planned visit. If a subject's planned visit assessment is out of the defined visit window and there is no unscheduled assessment within the same window, then this CRF collected planned visit assessment will be used for the analysis.

Period	Analysis Visit	Protocol Defined Window	Scheduled Study Day	Windows
Screening	Visit 1 (Screening)	-6 Weeks to Day -1	-41 to -1	<= -1
Treatment	Visit 2/ Randomization (Day 1)	Day 1	1	1
	Visit 3 (Week 4)	Week 4 ( $\pm 3$ days)	28	2, 42
	Visit 4 (Week 8)	Week 8 ( $\pm 3$ days)	56	43, 70
	Visit 5 (Week 12)	Week 12 ( $\pm 3$ days)	84	71, 98
	Visit 6/EOT (Week 16)	Week 16 ( $\pm 3$ days)	112	99, 119
Follow-up	Visit 7 (Follow-up)	Week 18 ( $\pm 3$ days)	126	$\geq 120$

If multiple records in the same analysis visit, the scheduled visit is preferred to the unscheduled visits, otherwise the one closest to the scheduled visit study day will be selected for the analysis and summaries. The later one is preferred if there are more than one record have the same distance to the scheduled study day.

In the derivation of post baseline extreme values (e.g., minimum, maximum, worst, last), all post baseline assessments will be included.

All data including additional unscheduled visits required for patients who need direct site assistance (due to AE monitoring, in order to fulfill screening requirements, and/or for safety maintenance) will be presented in subject listings unless otherwise specified.

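### SAP 3.4 pre-specifies no by-arm count of patients meeting the protocol's liver triggers, and its normal-range shift table cannot show worsening from an ALT or AST that is already raised

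*SAP*

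**What the plan says.** **Laboratory outputs.** SAP 3.4 plans four things.
- Visit summaries: "Laboratory results at each scheduled visit will be summarized by actual treatment group", with changes from baseline. SAP 2.1 sets the statistics as n, mean, SD, median, minimum and maximum.
- Out-of-range flags in the listings.
- Shift tables: "Shift tables for the shift from baseline with respect to the reference normal range will be provided".
- One further line: "Laboratory abnormalities of special interest will be summarized".

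Protocol 11.2.2.1.2 makes the same promise: "Values outside of the reference range will be flagged and laboratory abnormalities of special interest will be summarized". Neither document attaches a parameter or a threshold to it. Protocol 11.2.2.7 adds only this: "For each visit, the actual result, the change from Baseline, and the observed post-baseline value will be presented".

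**Liver monitoring.** Protocol 10.2.2.1 states: "Patients will be monitored as described below for drug-induced liver injury from randomization to 2 weeks following the last administration of study drug". The criteria are:
- ALT above 5 x ULN, or above 3 x baseline ("if ALT elevated at Baseline"), with a parallel rule for AST;
- total bilirubin above 2 x ULN, or above 1.5 x baseline if raised at baseline.

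Each criterion leads to repeat tests and, on confirmation, to interruption of study drug.

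**Handling of repeated values.** When several records fall in one analysis visit, SAP 2.3 says that "the scheduled visit is preferred to the unscheduled visits". The same section includes every post-baseline assessment when extremes are derived. SAP 3.2 tabulates post-baseline minima and maxima for ALT, AST and GGT as secondary efficacy variables.

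**The concern.** The protocol identifies possible liver injury by multiples of ULN and of baseline, and the SAP classifies laboratory results only as inside or outside the normal range. The two scales diverge in the patients this trial can enrol: protocol 7.2.2 (criterion 4a) admits ALT and AST up to 5 x ULN.

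No table, listing or AE category in the SAP names the 10.2.2.1 criteria or any multiple of ULN or baseline. The only AE of special interest is ischemic colitis (protocol 10.1.1.3). The SAP abbreviation list still carries a term for potentially clinically significant values, but no criteria and no table follow.

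Safety and tolerability is a secondary objective in a liver-disease population. With 23 patients per arm, the useful summary is how many in each arm met a trigger. If the open line in SAP 3.4 is defined only after unblinding, its thresholds will have been chosen with the data in view.

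**Working it through.** The plan has no figure to reproduce, so the check sets each trigger against the shift cell.

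**Inputs.** Trigger limbs from protocol 10.2.2.1; eligibility limits from protocol 7.2.2 (ALT or AST above 5 x ULN excluded; total bilirubin above ULN excluded except in Gilbert's syndrome); shift categories from SAP 3.4. The baseline multiples are illustrations, because the documents give no distribution.

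**ALT.** Let b be baseline in multiples of ULN. If b > 1, the trigger point is T = min(5, 3b). If b is 1 or less, T = 5.

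| b (x ULN) | T (x ULN) | Rise needed, T/b | Shift cell once T is passed |
|---|---|---|---|
| 0.8 | 5.0 | 6.25-fold | normal to high |
| 1.2 | 3.6 | 3.0-fold | high to high |
| 1.5 | 4.5 | 3.0-fold | high to high |
| 2 | 5.0 | 2.5-fold | high to high |
| 3 | 5.0 | 1.67-fold | high to high |
| 4 | 5.0 | 1.25-fold | high to high |

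For every b above 1, a patient who meets the trigger shares a cell with one whose ALT has not moved. For b = 0.8, a rise to 1.1 x ULN and a rise above 5 x ULN share the normal-to-high cell.

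**Bilirubin.** If b > 1, T = min(2, 1.5b); otherwise T = 2. At b = 1.2, T = 1.5 x 1.2 = 1.8. At b = 1.5, 1.5b = 2.25, so T = 2. Eligibility largely confines b > 1 to Gilbert's syndrome, so most patients would start normal and a rise would register. The table would still not separate a slight rise from one above 2 x ULN, and no count is planned.

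**Can the other outputs supply the count?**
- *Visit summaries.* An arm's maximum value or maximum change can reveal one extreme patient. It does not say how many met a criterion. Protocol 10.2.2.1 takes ULN by age and gender, so a maximum in raw units does not convert to one multiple of ULN or to a multiple of that patient's baseline.
- *Post-baseline extremes.* These use all assessments, so unscheduled peaks count. They are planned as summaries in raw units for ALT, AST and GGT; SAP 3.2 does not list total bilirubin.
- *ANCOVA and MMRM.* These compare mean changes.
- *AE tables.* Protocol 10.1.1.1 allows a finding that prompts further investigation to be an AE. Protocol 10.1.2 leaves that to the investigator and lets enzyme rises be absorbed into a diagnosis. SAP 3.4 tabulates AEs leading to discontinuation of treatment; it has no table for interruption, which is the action 10.2.2.1 specifies.

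**What a count would tell with 23 per arm.** Zero events leaves a two-sided exact 95% upper bound of 1 - 0.025^(1/23) = 14.8%. The chance of at least one event in an arm, 1 - (1 - p)^23, is 37%, 69% and 91% at assumed true rates of 2%, 5% and 10%.

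**The case against.** The other side has a good deal to say. The SAP promises a summary of laboratory abnormalities of special interest, and an undefined table is not an absent one. Visit summaries include medians and extremes of value and change, and change from baseline does not depend on the normal range. Unscheduled peaks enter the ALT and AST extremes. The preference for scheduled values does not hide a trigger first seen at a scheduled visit, because that value is kept and the 72-hour sample is only the repeat. Clinically significant rises can appear as AEs by arm. Section 10.2.2 concerns individual patient monitoring, nothing in protocol version 3.0 requires trigger counts, and with 23 per arm a descriptive table adds modest information.

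All of this stands, and it rules out three stronger readings that a reader might infer:
- That patients meeting the triggers will never be counted by arm. The open line in SAP 3.4 could include them; the defect is that nothing says it will.
- That a large rise could be found only in listings. An arm maximum, a maximum change or an AE could show it.
- That some large share of the 46 patients is affected. Multiplying 46 by a guessed proportion with raised ALT counts those whose upward change the shift table cannot register, not those who would meet a trigger. The documents support neither figure.

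What the objection does not supply is a pre-specified count of patients against ULN or their own baseline.

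**Conclusion.** The point holds as a gap in pre-specification. The SAP fixes no by-arm count of patients meeting the 10.2.2.1 criteria, leaves its one potentially relevant summary undefined, and relies for categories on a table that cannot show worsening from a raised ALT or AST or grade a rise from a normal one. For bilirubin, the high-to-high problem is largely limited to Gilbert's syndrome; the gap there is the missing count.

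The shift-table limitation follows from the definitions and does not depend on the illustrative baselines. Its practical size is unknown, since the documents give no baseline ALT or AST distribution and no expected trigger rate. It affects descriptive safety reporting only, not the primary efficacy analysis. It is worth correcting because the correction is cheap and should be settled before treatment codes are seen.

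**What to change.** In SAP 3.4, Laboratory Tests:
1. Define laboratory abnormalities of special interest to include the number and percent of patients, by actual treatment, with any post-baseline value, scheduled or unscheduled, that meets each ALT, AST and total bilirubin criterion exactly as written in protocol 10.2.2.1. Show the ULN limb and the baseline limb separately, with a supporting listing.
2. Present the ALT and AST shift tables in categories of multiples of ULN.
3. Hold back any count of triggers confirmed on repeat until protocol 10.2.2.1 has been reconciled: its bilirubin paragraph makes the next step depend on confirming a liver enzyme elevation, although the trigger is bilirubin. The AST baseline limb also lacks the greater-than sign that the ALT limb has, so the sponsor should state how it is read before programming.

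The cost is SAP wording and one or two descriptive tables from data already collected. No visit, test, clinical threshold or management rule changes.
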